4.5. Analysis Windowing Rules

In the study, each patient has variable length of the DB periods, i.e., 33-36 months, depending on the enrollment time. For the analysis of all-cause mortality in different analysis periods, the Survival Follow-up Time is calculated as time from the first dose of study drug to the last Survival Follow-up date, following the windowing rules summarized as in [Table 2](#). For the analysis of composite outcome all-cause mortality and CV events in different analysis periods, the Event Follow-up Time is calculated as time from the first dose of study drug to the last Event Follow-up date, following the windowing rules summarized as in [Table 3](#).

For all longitudinal efficacy assessments, if a scheduled post-baseline assessment is not performed, another assessment performed within the Visit Window will be grouped with the scheduled assessment for analysis (Table 4 and Table 5). If there are two or more such assessments within a Visit Window, the assessment closest to the Target Visit Day will be used as the analysis value for that visit. If there are multiple visits with the same distance from the Target Visit Day, the earliest visit will be selected.

Table 2: Definition of Last Survival Follow-up Date in the Analysis of All-cause Mortality for Different Analysis Periods

Analysis Period	Patients who enter OLE	Patients who do not enter OLE
During the DB period	First dose of OLE	Earlier of last known alive/death date and first DB dose date + 1120 days
During the DB + 6 months OLE period	Earlier of last known alive/death date and the first OLE dose date + 183 days	Earlier of last known alive/death date and first DB dose date + 1303 days
During the Study	Last known alive/death date	

Note: Dates after analysis cutoff date will be replaced by the cutoff date. 1120 days are calculated as 36 months (156 weeks) plus 4 weeks. 1303 days are calculated as 1120 days plus 6 months (e.g., 183 days).

Table 3: Definition of Last Event Follow-up Date in the Analysis of Composite Outcome for Different Analysis Periods

Analysis Period	Patients who enter OLE	Patients who do not enter OLE
During the DB period	First dose of OLE	Earliest of last known alive/death date, study discontinuation date, and first DB dose date + 1120 days
During the DB + 6 months OLE period	Earliest of last known alive/death date, study discontinuation date, last dose date + 365 days and the first OLE dose date + 183 days	Earliest of last known alive/death date, study discontinuation date, and first DB dose date + 1303 days
During the Study	Earlier of last known alive/death date and study discontinuation date	

Note: For patients who died within 30 days of study discontinuation date, the study discontinuation date will be set as the death date. Dates after analysis cutoff date will be replaced by the cutoff date. 1120 days are calculated as 36 months (156 weeks) plus 4 weeks. 1303 days are calculated as 1120 days plus 6 months (e.g., 183 days).

Table 4: Analysis Visit Windows for Longitudinal Efficacy Endpoints in the DB period

Analysis Visit Label	Target Day	Visit Window (days, inclusive)				
		6-MWT, KCCQ, NYHA, CCI	CCI	CCI	CCI	CCI
Month 3 (Week 12)	85	N/A	CC	[43, 126]	CC	

Analysis Visit Label	Target Day	Visit Window (days, inclusive)				
		6-MWT, KCCQ, NYHA, CCI	CCI	CCI	CCI	CCI
Month 6 (Week 24)	169	[85, 252]	N/A	[127, 210]	CCI	CCI
Month 9 (Week 36)	253	N/A	N/A	[211, 294]	CCI	CCI
Month 12 (Week 48)	337	[253, 420]			CCI	
Month 18 (Week 72)	505	[421, 630]			CCI	CCI
Month 24 (Week 108)	757	[631, 840]				
Month 30 (Week 132)	925	[841, 1016]				

Table 5: Analysis Visit Windows for Longitudinal Efficacy Endpoints in the OLE period

Analysis Visit Label	Target Day	Visit Window (days, inclusive)		
		KCCQ, CCI	NYHA	CCI
OLE Day 1	1	N/A		N/A
OLE Month 6 (Week 24)	169	[85, 252]		[85, 210]
OLE Month 9 (Week 36)	253	N/A		[211, 294]
OLE Month 12 (Week 48)	337	[253, 420]		[295, 420]
OLE Month 18 (Week 72)	505		[421, 588]	
OLE Month 24 (Week 96)	673		[589, 756]	

Note: the target day and visit windows for OLE period is relative to the first dose date in OLE period.

For PD and safety parameters, the reported eCRF visits will be used for by-visit analysis. Only scheduled assessments will be included in by-visit summaries of these parameters.

4.6. Multiple Comparisons/Multiplicity Procedure

The overall Type I error rate for the two primary endpoints and secondary endpoints will be controlled at a 2-sided 0.05 significance level using a prespecified multiplicity testing procedure as described in [Figure 2](#). Each primary and secondary endpoint defined in the vutrisiran monotherapy subgroup and overall population is considered as a family, e.g., 6-MWT in vutrisiran monotherapy subgroup and overall population. There are 5 families in total. The primary endpoint family and the first three secondary endpoint families will be tested using a truncated Hochberg test with a truncation fraction of 0.96, and the last secondary endpoint family will be tested using a regular Hochberg test. This Hochberg-based gatekeeping procedure was

based on an extension of the general mixture methodology [Dmitrienko 2011; Dmitrienko 2013]. The details of this multiple testing procedure are described below.

Step 1 (primary endpoint family)

The two primary endpoints will be tested at a 2-sided 0.05 significance level using the truncated Hochberg testing procedure with a truncation factor of 0.96.

- i. If the larger of two p-values is ≤ 0.049 , reject both null hypotheses and continue to Step 2a.
- ii. If the larger p-value is > 0.049 and the smaller p-value is ≤ 0.025 , reject the null hypothesis corresponding to the smaller p-value and continue to Step 2b.
- iii. If the larger p-value is > 0.049 and the smaller p-value is > 0.025 , accept both null hypotheses and stop the testing procedure.

Step 2 (6-MWT family)

The overall significance level used in the 6-MWT family is determined by the number of significant tests in Step 1.

Step 2a: If both null hypotheses are rejected in Step 1, test following the same steps i, ii, and iii as for the primary endpoint family.

Step 2b: If only one null hypothesis is rejected in Step 1, only test the 6-MWT defined in the same population as the corresponding rejected null hypothesis in Step 1.

- i. If the p-value is ≤ 0.001 , reject the null hypothesis and continue to test the next secondary endpoint defined in the same population.
- ii. If the p-value is > 0.001 , accept the null hypothesis and stop the testing.

For the KCCQ-OS and all-cause mortality families, the Step 3 and Step 4 are the same as that described in Step 2. For the NYHA class family, the Step 5 is described as below.

Step 5 (NYHA class family)

[figure not shown]
Step 5a: If both null hypotheses are rejected in Step 4, then the two NYHA class endpoints will be tested as follow.

- i. If the larger of two p-values is ≤ 0.05 , reject both null hypotheses.
- ii. If the larger p-value is > 0.05 and the smaller p-value is ≤ 0.025 , reject the corresponding null hypothesis of the smaller p-value.
- iii. If the larger p-value is > 0.05 and the smaller p-value is > 0.025 , accept both null hypotheses.

Step 5b: If only one null hypothesis is rejected in Step 4, only the NYHA class defined in the same population as the corresponding rejected null hypothesis in Step 4 will be tested.

- i. If the p-value is ≤ 0.001 , reject the null hypothesis.
- ii. If the p-value is > 0.001 , accept the null hypothesis.

Figure 2: Multiplicity testing procedure for testing primary and secondary endpoints

4.7. Handling of Missing Data

No imputation will be done for early dropout patients for the primary analysis of the composite outcome endpoint. For longitudinal endpoints including 6-MWT and KCCQ-OS, the primary analyses will be based on mixed effects model repeated measures (MMRM) which implicitly impute missing values assuming missing at random (MAR). The only exception is missing due to death and unable to walk due to progression of ATTR amyloidosis (for 6-MWT only). For NYHA class, the missing due to death will also be imputed as class IV, and missing due to other reasons will be imputed via multiple imputation. Data handling strategies for these aforementioned intercurrent events and other intercurrent events in the primary analysis of 6-MWT, KCCQ and NYHA class are detailed in Section 5.7.2.1 and Section 5.7.2.3, respectively. Sensitivity analysis of the composite outcome endpoint will be conducted using Multiple Imputation (MI) to handle missing data, as described in Section 5.7.1.4.4. Sensitivity analyses for 6-MWT and KCCQ-OS will be conducted based on a pattern mixture model (PMM) which assume missing not at random (MNAR), as described in Section 5.7.2.1.3.

Since baseline NT-proBNP will be used as a covariate in the statistical models, for one patient with missing baseline NT-proBNP, the baseline value will be imputed with Week 12 visit data.

4.8. Categorization of Death, Hospitalizations and Urgent HF Visits

The details about the adjudication process for hospitalizations and urgent HF visits were specified in the Clinical Events Committee (CEC) Charter. Specifically, the CEC will adjudicate all non-elective (urgent/emergency/unscheduled) cardiovascular (CV) and non-cardiovascular (non-CV) hospitalizations/emergency department visits and all urgent, unscheduled office or outpatient visits for heart failure (urgent HF visits) occurring after randomization. Elective (scheduled/non-urgent/non-emergency) CV hospitalizations and non-CV hospitalizations are not events of special interest in this trial. However, these will also be reviewed by the CEC to ensure

that potential non-elective hospitalizations have not been missed. All deaths will be adjudicated, including those that are collected after a subject permanently discontinues the study (e.g., publicly available death records).

Investigators also record their assessment of each inpatient admission or urgent/unscheduled healthcare visit on the eCRF. Hospitalizations and urgent HF visits based on the Investigator's assessment are defined as follows:

- Hospitalizations are defined as non-elective hospitalizations or visits (excluding home visits) requiring overnight stay (i.e., discharge date at least one day after admission date). The exact times of admission/discharge are not collected in the eCRF; therefore, the 24-hour stay criteria cannot be applied. For each hospitalization, the investigator provides their classification of CV versus non-CV.
- Urgent HF visits are defined as non-elective visits (including home visits) that are not classified as hospitalizations based on the above definition, but meet the following criteria:
 - Heart failure is the primary reason for the visit per the Investigator.
 - IV diuretics administered during the visit.

CCI

CCI

CCI

5. PRIMARY STATISTICAL ANALYSES

The primary objective of this study is to evaluate the efficacy and safety of vutrisiran compared with placebo. Analyses described in this section focus on this objective.

5.1. Patient Disposition

The number and percentage of patients in the following categories will be summarized by randomized treatment arm and overall:

- Randomized

- Treated
- Completed Month 30 (Week 132) visit
- Completed the DB Period
- Discontinued treatment in the DB period and primary reason for treatment discontinuation
- Discontinued study in the DB period and primary reason for study discontinuation
- Entered the OLE period
- Discontinued treatment in the OLE period and primary reason for treatment discontinuation
- Discontinued study in the OLE period and primary reason for study discontinuation

The number and percentage of patients enrolled by country and site will also be summarized.

5.2. Demographics and Baseline Characteristics

Demographic and baseline disease characteristics will be summarized using the FAS.

Age at randomization, height, weight, and body mass index (BMI) will be summarized using descriptive statistics. Age group (<65; \geq 65 - <75; \geq 75), sex, race, ethnicity, and region (US; Europe; rest of world) will be summarized by presenting the frequencies and percentages of patients in each category.

The following baseline disease characteristics will be summarized by presenting the numbers and percentages of patients in each category:

- ATTR disease type [hATTR; wtATTR]
- Baseline tafamidis use [Yes; No]
- NYHA Class [I; II; III]
- NYHA Class I/II and age < 75 years [Yes; No]
- ATTR amyloidosis disease stage [1; 2; 3]
- CCI [REDACTED]
- Previous HF hospitalization [Yes; No]
- NT-proBNP (\leq 3000; >3000 ng/L)

The age at symptom onset and the time in years since hATTR or wtATTR diagnosis will be summarized, overall and by ATTR disease type, using descriptive statistics. For those who previously used tetramer stabilizers, the time from discontinuation of tetramer stabilizer to the start of study drug will be summarized using descriptive statistics. For patients in the baseline tafamidis subgroup (per the clinical database), the time from the start of tafamidis therapy to the start of study drug will be summarized using descriptive statistics.

The number and percent of patients with each ATTR disease type and with each genotype (for hATTR patients) will be summarized by country and treatment arm.

5.3. Medical History

Medical history and prior procedures reported will be coded using the Medical Dictionary for Regulatory Activities (MedDRA), version 23.0 or newer. Unique patients who report medical history events will be summarized by MedDRA system organ class (SOC), high level term (HLT) and preferred term (PT). Other medical history data including cardiac medical history, neuropathy history, historical surgeries/procedures in the past 12 months and historical inpatient admissions or urgent healthcare visits in the past 12 months will also be summarized. Medical history data will be summarized using the FAS and presented in data listings as well.

5.4. Protocol Deviations

Protocol deviations will be classified by medical review prior to database lock, and protocol deviations will be identified in the protocol deviation file. A major protocol deviation is a deviation that may significantly impact the completeness, accuracy, and/or reliability of the trial data; that may significantly affect a subject's rights, safety, or well-being (ICH E3. Guideline: Structure and content of Clinical Study Reports Questions & Answers (R1). 2012).

The Sponsor or designee will be responsible for identifying and reporting the protocol deviations into the protocol deviation file. This file will include a description of each protocol deviation and whether each deviation is classified as major. The file also contains an identifier about if a protocol deviation is related to COVID-19 pandemic. The file will be reviewed and finalized prior to database lock.

Major protocol deviations will be summarized for all randomized patients. All protocol deviations, major protocol deviations, and those related to COVID-19 will be listed.

5.5. Study Drug Exposure and Compliance

Exposure to study drug in months and the number of doses of study drug received will be summarized using the Safety Analysis Set for the DB period. Summaries of the numbers and percentages of patients with no missing doses, and the number of missing doses per patient will also be provided.

The last date of exposure to study drug during the DB period is defined as the earliest of the following dates:

- Last dose date + 83 days (the dosing interval is 84 days)
- Analysis cutoff date
- End of study date
- OLE Day 1 Dose date (start of OLE period)

Duration of exposure (month) is defined as: (the last date of exposure to study drug – date of the first dose +1)/30.4375. Dose interruptions and compliance are not taken into account for duration of exposure. Study drug exposure data collected in the electronic case report form (eCRF) of study drug administration will be listed.

5.6. Prior and Concomitant Medications/Procedures

Medications will be coded using the World Health Organization Drug Dictionary (March 2019 or later); and procedures will be classified by the MedDRA coding system (version 23.0 or later).

Medications will be classified as prior and/or concomitant. Prior medications are those medications with start date prior to the first dose of study drug, regardless of medication end date. If the medication end date is before the date of first dose of study drug, the medication will be summarized as prior medication regardless of whether the start date is missing or not. Concomitant medications are medications, other than the study drug, that have a start date on or after the date of first dose of study drug, as well as medications that started before the date of first dose of study drug and are ongoing after the first dose of study drug (or have an imputed end date after the first dose of study drug) and through the first dose in the OLE period for patients who entered OLE, or the earlier of (84 days after the last dose of study drug, early study discontinuation) for patients who discontinued DB treatment for the outputs during the DB period. Unique patients who reported medications will be summarized by Anatomical Therapeutic Chemical (ATC) level 3 class (or level 2 if not available) and PT. Summaries will be provided for prior and concomitant medications separately using Safety Analysis Set.

Similarly, procedures will be classified as prior and/or concomitant. Unique patients who report procedures during the DB period will be summarized by MedDRA system organ class (SOC), high level term (HLT) and preferred term (PT).

When there are partial or missing dates, imputed dates will be used to determine 1) if a medication/procedure is prior or concomitant, and 2) duration of exposure to select medications/procedures, as needed. Imputed dates will not be presented in the listings. The imputation rule is documented in Appendix 9.7.

For patients who are not on baseline tafamidis, tafamidis drop-in after the date of the first dose of study drug will be summarized, including but not limited to: number and percent of patients with drop-in as well as descriptive statistics for the time from the first dose of study drug to the tafamidis drop-in.

For patients who are taking tafamidis at baseline, tafamidis disease progression signs and symptoms prior to the baseline will be summarized.

CCI

5.7. Efficacy Analyses

Efficacy endpoints will be analyzed using the FAS and mono-FAS. As an important subgroup, efficacy endpoints will also be analyzed in the background tafamidis subgroup. Therefore, unless otherwise specified, all efficacy analyses will be presented by treatment groups in the overall population, vutrisiran monotherapy subgroup and background tafamidis subgroup. The vutrisiran monotherapy subgroup and background tafamidis subgroup analyses are based on subgroup data only. In general, the same statistical model will be used for analyzing the efficacy endpoint for overall population, the vutrisiran monotherapy subgroup and the background tafamidis subgroup,

with the exception that in the analysis of the overall population, baseline tafamidis use will be used as an additional covariates or stratification factor.

For covariates used in the statistical models, unless noted otherwise, the categorizations will be based on ATTR disease type (hATTR vs. wtATTR), NYHA Class (I/II vs. III), age group (<75 vs. >=75) and baseline NT-proBNP group (<=3000 ng/L, >3000 ng/L). **CCI**

For composite endpoints, mean cumulative function (MCF) plots by treatment groups will be generated. For longitudinal endpoints, least square mean (+/- SEM) over time by treatment groups will be plotted. For time to event endpoints, Kaplan-Meier (KM) plots by treatment groups will be generated.

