5.7.1.2. Primary Analysis

The primary endpoint of all-cause mortality and recurrent CV events CCI [REDACTED]

CCI

The primary analysis will include events occurring during the DB period. For each patient, the Event Follow-up time will be calculated as the time from the first dose of study drug to the last Event Follow-up date (Table 3). Deaths collected after study discontinuation are not included in the analysis.

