5.7.1.3. Component Analysis

The primary endpoint includes 2 components: all-cause mortality and recurrent CV events. The following will be summarized: the number of all-cause mortality (including death, heart transplant, and LVAD), the number of CV events (including CV hospitalization, indeterminate hospitalization, and urgent HF visit), the number and percentage of patients with at least one event. Vital status data after study discontinuation is not included in the above mortality component descriptive summary.

Inferential analyses for the component of all-cause mortality will include the vital status data collected after study discontinuation. The same statistical methods as that for the secondary endpoint of all-cause mortality (Section 5.7.2.2) will be used.

Inferential analyses for the component of recurrent CV events will be based on Poisson regression model with covariates including treatment, ATTR disease type, NYHA Class, age group, and baseline NT-proBNP as covariates, adjusting for the event follow-up time (i.e., including this duration as an offset). The overall population analysis will also include baseline tafamidis use and treatment-by-baseline tafamidis use interaction as covariates.

Recurrent CV events will be also analyzed using a joint frailty model (JFM) [Rondeau 2007] as a sensitivity analysis. For the JFM, the same covariates will be included for both the sub-model for recurrent CV events and the sub-model for all-cause mortality: treatment, ATTR disease type, NYHA Class, age group and baseline NT-proBNP group. The overall population analysis will also include baseline tafamidis use as a covariate. The baseline hazard functions for both recurrent CV events and all-cause mortality are approximated by piecewise constant functions. Details of the JFM methodology and implementation are provided in Appendix 9.6 .

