5.7.4. Evaluation of Subgroups

All analysis and summary results are presented by baseline tafamidis use subgroups, with vutrisiran monotherapy subgroup defined as an analysis population and background tafamidis defined as a key subgroup. Additionally, subgroup analyses will be conducted to assess the consistency of treatment effect within various subgroups defined by baseline characteristics as listed in the following table.

Subgroup	Overall population	Vutrisiran Monotherapy subgroup
Baseline tafamidis use (yes; no)	Yes	N/A
Age group (<75; ≥75)	Yes	Yes
ATTR disease type (hATTR; wtATTR)	Yes	Yes
NYHA class (I/II; III)	Yes	Yes
Baseline NT-proBNP (≤2000; >2000 ng/L)	Yes	Yes

Subgroup analyses will be performed for the composite endpoint of all-cause mortality and recurrent CV events, 6-MWT, KCCQ-OS, all-cause mortality, NYHA class, and recurrent CV events in both the overall population and vutrisiran monotherapy subgroup. The analyses will be conducted based on the subgroup data only.

- Composite endpoint of all-cause mortality and recurrent CV events:

Composite endpoint of all-cause mortality and recurrent CV events will be analyzed by LWYY model including treatment and baseline NT-proBNP as covariate. For subgroup analysis in the overall population, the model will also be stratified by baseline tafamidis use.

- Change from baseline in 6-MWT and KCCQ-OS:

Change from baseline in 6-MWT and KCCQ-OS will be analyzed by MMRM model with baseline value as a covariate, and treatment, visit, treatment-by-visit interaction as fixed effects. For subgroup analyses in the overall population, the model will also include baseline tafamidis use as a fixed factor.

- CCI [REDACTED]

- Change from baseline in NYHA class:

The binary outcome (stable or improved vs. worsened in NYHA Class at Month 30) will be analyzed by a CMH method stratified by baseline NT-proBNP. For subgroup analysis in the overall population, the model will also be stratified by baseline tafamidis use.

- Recurrent CV events:

The frequency of CV events will be analyzed by Poisson regression including treatment and baseline NT-proBNP as covariates. For subgroup analysis in the overall population, the model will also include baseline tafamidis use as a covariate.

Forest plots will be generated to illustrate the estimated treatment effect along with 95% CI within each subgroup.

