For patients who discontinued study in Interval 2, only the interval from the study discontinuation to the last survival follow-up date in the DB period will be imputed. The imputation steps are similar as Interval 1.

- **For patients who discontinued study in either Interval 1 or Interval 2 and died in Interval 2 (type 3):**

For each patient, The imputation steps are similar as above.

The above 2-stage MI process will be repeated for 500 times, e.g., 500 imputed datasets. For each imputed dataset, the same LWYY model as the primary analysis will be applied. The results will finally be combined using Rubin's rule [Rubin 1987].

Sample SAS Code:

Stage 1 (CV event rate estimation model):

Poisson model will be used to fit CV event data and will then be used to impute the missing data. The “OFFSET” in the linear model implemented by PROC GENMOD is the adjustment for the event follow up time in the interval (those who entered the interval but did not complete through).

```
proc sort data=tot; by flg_dthevt_p1 trt01p tafabs1; run;
proc mcmc data=tot outpost=mcmc_p1 nmc=500 propcov=quanew nbi=2000
mintune=500 seed=7;
  ods select PostSumInt;
  array data[2] 1 logbnp;
  array beta[2] alpha beta_logbnp;
  parms alpha beta:;
  prior alpha beta: ~ normal(0, prec = 1e-6);
  call mult(data, beta, mu);
  model nevt_p1 ~ poisson(exp(mu+logdur_p1));
  by flg_dthevt_p1 trt01p tafabs1;
run;
```

where variable ‘nevt_p1’ is the number of cv events during Interval 1, ‘logdur_p1’ is the log transformation of the event follow up time in Interval 1.

For Interval 2, the model covariates will also include ‘ncv1’ as an additional model term for the number of the cv events occurring during the Interval 1.

Stage 2 (event time imputation model):

The macro below can be used to perform the multiple imputation to generate the predicted missing event time.

```
data aftersample;
  /* Set the seed for reproducibility */
  call streaminit(1234);
  set needimput;
  /* Generate random event times until cumulative time reaches the end of the
interval */
```

```
time = 0;
cumulative_time = 0;
event_count = 0;

/* Loop until cumulative time reaches the end of the interval */
do while (cumulative_time < gapfu);
  /* Generate random event time from exponential distribution */
  time = rand("Exponential", 1/rate);
  /* Update cumulative time */
  cumulative_time + time;

  /* Output the result for each event */
  if cumulative_time < gapfu then do;
    event_count + 1;      output;

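### SAP 5.7 codes baseline NT-proBNP by default as two groups cut at 3000 ng/L, while Appendix 9.3 uses its logarithm; log NT-proBNP as the regression default would settle the coding and regain modest precision

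*SAP*

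**What the plan says.** SAP 5.7 gives a general rule: "For covariates used in the statistical models, unless noted otherwise, the categorizations will be based on ATTR disease type" and three further factors, the last being "baseline NT-proBNP group (<=3000 ng/L, >3000 ng/L". Redacted text follows directly. SAP 4.7 confirms a general role for the marker ("Since baseline NT-proBNP will be used as a covariate in the statistical models") without giving its form.

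The analyses that can be read fall into four sets:

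- **Cut at 3000 ng/L, regression or imputation.** The joint frailty model in 5.7.1.3 lists "treatment, ATTR disease type, NYHA Class, age group and baseline NT-proBNP group". The pattern-mixture imputation model in Appendix 9.4 states the same two groups.
- **Cut at 3000 ng/L, stratification.** The win ratio (5.7.1.4.1, Appendix 9.2) is stratified by NT-proBNP group, as is the CMH analysis of survival rates (5.7.2.2.3). The CMH analysis of NYHA class (5.7.2.3.2) is stratified by baseline NT-proBNP.
- **Log value.** The sample code for imputing CV events in Appendix 9.3 has "array data[2] 1 logbnp" and "array beta[2] alpha beta_logbnp". The text describing that model says only baseline NT-proBNP.
- **Form not stated.** This set holds the Poisson model for recurrent CV events (5.7.1.3), the LWYY and Poisson subgroup models (5.7.4), the NYHA MMRM (5.7.2.3.3) and the NYHA imputation model (Appendix 9.5).

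SAP 5.7.4 also plans subgroups by "Baseline NT-proBNP (≤2000; >2000 ng/L".

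The primary models cannot be read. In 5.7.1.2 the opening sentence breaks off at the redaction: "The primary endpoint of all-cause mortality and recurrent CV events CCI". The models in 5.7.2.1.2 (6-MWT and KCCQ-OS) and 5.7.2.2.2 (all-cause mortality) are also redacted.

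**The concern.** NT-proBNP is the one prognostic covariate, besides baseline tafamidis use, that the SAP carries into the LWYY and Poisson subgroup models. Splitting a continuous marker in two treats all patients on one side of the cut as equal and discards the prognostic differences among them. Weaker adjustment means wider confidence intervals from the same patients.

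The labelling adds a second problem. A programmer who follows 5.7 would code the unlabelled term as two groups; one who follows the code in Appendix 9.3 would use the logarithm. In the subgroup analyses this choice decides whether patients at or below 2000 ng/L receive any NT-proBNP adjustment.

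**Working it through.** **1. The subgroup at or below 2000 ng/L (no assumptions about effect size).** Suppose the 5.7 default applies to the models in 5.7.4. Every patient at or below 2000 ng/L is also at or below 3000 ng/L, so the two-group covariate takes one value and drops out. Above 2000 ng/L it still separates patients up to 3000 from those above. One row of the forest plot is then unadjusted for NT-proBNP and the other adjusted, for both the LWYY and the Poisson analysis. The NYHA CMH analysis likewise has a single NT-proBNP stratum in the lower subgroup.

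**2. Precision by formula.** The SAP gives no figure to reproduce, and the sample-size inputs are redacted. Everything in steps 2 and 3 is illustrative except N, allocation, follow-up length and the tafamidis share.

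Let log NT-proBNP be normal with median m and standard deviation s, and let its relation to outcome be log-linear. With c = [ln(3000) − ln(m)]/s and p the share of patients above 3000 ng/L, the share of the signal kept by the cut is R = φ(c)²/[p(1−p)]. If the log value explains a fraction r² of outcome variance, the variance ratio, cut to log, is (1 − r²R)/(1 − r²).

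Example, m = 2000 and s = 0.9: c = 0.405/0.9 = 0.45, p = 0.33, R = 0.591. At r² = 0.10 the ratio is (1 − 0.0591)/0.90 = 1.045.

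Over m = 1500, 2000 and 3000 and s = 0.7, 0.9 and 1.1, R runs from 0.44 to 0.64:

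| r² | Variance ratio, cut to log |
|---|---|
| 0.05 | 1.019 to 1.029 |
| 0.10 | 1.040 to 1.062 |
| 0.20 | 1.091 to 1.140 |

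**3. Power by simulation.** The model was a Poisson regression with robust standard errors and a log follow-up offset, standing in for the redacted primary model. There were 1000 trials per setting.

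- From the documents: N = 600, 1:1 allocation and 33 to 36 months of follow-up. With about 40% on tafamidis at baseline (Protocol 10.4.1), the monotherapy subgroup is 600 × 0.60 = 360.
- Assumed: rate ratio 0.72, 0.4 events per year on placebo, gamma frailty variance 1, drop-out 0.10 per year, m = 2000, s = 0.9, and a coefficient b per log unit of 0.4 or 0.7.

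| N | b | Power: log | Power: cut | Power: unadjusted | Empirical variance ratio, cut to log |
|---|---|---|---|---|---|
| 600 | 0.4 | 0.736 | 0.722 | 0.709 | 1.033 |
| 600 | 0.7 | 0.690 | 0.654 | 0.621 | 1.046 |
| 360 | 0.4 | 0.473 | 0.478 | 0.455 | 1.011 |
| 360 | 0.7 | 0.493 | 0.447 | 0.424 | 1.099 |

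Each power figure carries simulation error of about ±0.03. The log coding gained 1.4, 3.6, −0.5 and 4.6 points; the negative value is no difference within error. Mean treatment estimates under the two codings agreed to within 0.002 on the log scale. In every row the cut did better than no adjustment.

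**The case against.** A reader might infer that the primary analysis is shown to use the cut and to lose power by it. The documents do not support that. The rule in 5.7 allows exceptions, redacted text follows it, and the primary composite, 6-MWT/KCCQ-OS and mortality models cannot be read. The only visible regression or imputation models stated to use the cut are the joint frailty model and the pattern-mixture imputation, both sensitivity analyses. The unlabelled term elsewhere may already mean the log value, as it does in Appendix 9.3.

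Nor can it be said that the cut has no benefit. It assumes no log-linear relation, it matches the baseline table in 5.2, and the win ratio and CMH analyses need categories. The calculations favour the logarithm by construction, because the assumed relation is log-linear. They also omit NYHA class, age and ATTR type, which the Poisson and joint frailty models include; any overlap with NT-proBNP would shrink the loss. The joint frailty model represents unexplained heterogeneity directly, so the simulation does not carry over to it without qualification.

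All of this stands, and it limits the point to a modest gain in efficiency. It does not remove the point. The default is visible, the forms and labels differ between models, and the SAP already relies on log-linearity when it imputes CV events. A cut is also a strong assumption of its own: a single step at 3000 ng/L. The subgroup mismatch costs adjustment in one subgroup, and the treatment estimate there stays valid.

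**Conclusion.** The concern holds as one of efficiency and specification. A prespecified baseline cut is valid and raises no issue of bias or Type I error. As a default for regression and imputation models it is less efficient than the log value. The formula puts the variance cost at about 2 to 14%, and the simulation at about 1 to 10%, with 0 to 5 points of power. These sizes rest on assumed NT-proBNP distributions, prognostic strengths and event rates, none of which the documents give. They apply to the primary endpoints only if the redacted models use the cut. The uneven adjustment of the two NT-proBNP subgroup rows follows by logic, but only if the 5.7 default governs 5.7.4.

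**What to change.** In SAP 5.7, state that baseline NT-proBNP enters as a log-transformed continuous covariate in every regression or imputation model that contains it:

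- the Poisson and joint frailty models (5.7.1.3);
- the LWYY and Poisson subgroup models (5.7.4);
- the NYHA MMRM (5.7.2.3.3);
- the pattern-mixture and NYHA imputation models (Appendices 9.4 and 9.5);
- the redacted primary models, if they use the cut.

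Align the joint frailty and Appendix 9.4 wording, and have the Appendix 9.3 text say log NT-proBNP as its code does. Keep the 3000 ng/L groups for the win ratio and CMH analyses, and note that the NYHA CMH analysis then has one NT-proBNP stratum in the subgroup at or below 2000 ng/L. The ANCOVA in Appendix 9.4 and the 6-MWT/KCCQ-OS subgroup MMRM contain no NT-proBNP and need no change.

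The cost is one sentence in 5.7, matching edits to the model descriptions and a changed covariate line in the programs, all before unblinding. No new data are needed: SAP 4.7 reports one missing baseline value and already says how to fill it. The small downside is reliance on a log-linear relation.
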